## Appendix F(a): Infant' (English version)

University of Malaya

E

### Instrument : INFANT

Dear Madam,

Thank you for agreeing to participate in the research.

The purpose of this research is to evaluate the effectiveness of Kangaroo Care (KC) among mother with premature infant in NICU.

The questionnaire consists of:

Part I : Demographic Characteristic

Part II : Infant Progress Data Sheet (KCRP Booklet)

Please answer **ALL** the questions of your ability and as honestly as possible. Thank you for your cooperation and support in this research.

## Part I : Demographic Characteristic

1. Gender

01. Male  02. Female

2. Race

01. Malay  02. Chinese  03. Indian   
04. Other \_\_\_\_\_ (*please specify*)

3. Post-natal age (days) \_\_\_\_\_ (*please specify*)

4. Gestation age at birth (weeks) \_\_\_\_\_ (*please specify*)

5. Birth weight(kg) \_\_\_\_\_ (*please specify*)

6. Mode of feeding status

01. Tube feeding  02. Spoon-feed  03. Breastfeeding

7. Type of milk

01. Express Breast Milk (EBM)  02. Breastfeeding  03. Formula milk

8. Initiate breastfeeding (weeks) \_\_\_\_\_ (*please specify*)

9. Discharge on breastfeeding (weeks) \_\_\_\_\_ (*please specify*)

10. Weaned exclusive breastfeeding (months) \_\_\_\_\_ (*please specify*)

## Appendix F(b) : Infant's (Infant KCRP Booklet)

### Instrument : INFANT (English Version )

Dear Madam,

Thank you for agreeing to participate in the research.

The purpose of this research is to evaluate the effectiveness of Kangaroo Care (KC) among mother with premature infant in NICU.

The questionnaire consists of:

Part I : Demographic Characteristic

Part II : Infant Progress Data Sheet (KC Booklet)

Please answer **ALL** the questions of your ability and as honestly as possible. Thank you for your cooperation and support in this research.

## Part I : Demographic Characteristic

1. Gender

01. Male  02. Female

2. Race

01. Malay  02. Chinese  03. Indian

04. Other \_\_\_\_\_ (please specify)

3. Post-natal age (days) \_\_\_\_\_ (please specify)

4. Gestation age at birth (weeks) \_\_\_\_\_ (please specify)

5. Birth weight(kg) \_\_\_\_\_ (please specify)

6. Mode of feeding status

01. Tube feeding  02. Spoon-feed  03. Breastfeeding

7. Type of milk

01. Express Breast Milk (EBM)  02. Breastfeeding  03. Formula milk

8. Initiate breastfeeding (weeks) \_\_\_\_\_ (please specify)

9. Discharge on breastfeeding (weeks) \_\_\_\_\_ (please specify)

10. Weaned exclusive breastfeeding (months) \_\_\_\_\_ (please specify)

## Part II : Infant progress data sheet for experimental group

Day (D)	D0	D1	D2	D3	D4	D5	D6	D7	D8	D9	D10 Till discharge	Remarks
Infant number :												
Temperature (Pre/Post) KC												
KC (in minutes or hours/day)												
Weight gain velocity (g/days)												
Feeding (EBM or Breastfeeding)												
Wean BF (weeks)												

D = Day, 0 = Birth, KMC = Kangaroo Mother Care, ↑= Increase & ↓=Decrease and Breastfeeding, EBM = Express Breast Milk

## Appendix H : Nurse's Questionnaire

University of Malaya

### QUESTIONNAIRE II : NURSES

Dear Nurses,

Thank you for agreeing to participate in the research.

The purpose of this research is to evaluate the effectiveness of Kangaroo Care (KC) among mother with premature infant in NICU.

The questionnaire consists of:

Section A : Demographic Characteristic

Section B : Part I - Perception on KC

Part II - Knowledge on KC

Part III - Practice on KC

Please answer **ALL** the questions to the best of your ability and as honestly as possible.

Thank you for your cooperation and support in this research.

## Section A : Demographic Characteristic

Instruction : Please ✓ the response.

1. Age \_\_\_\_\_ (*please fill in the blank*)

### 2. Gender

01. Male  02. Female

### 3. Race

01. Malay  02. Chinese  03. Indian  04. Others-  
\_\_\_\_\_ (*please specify*)

### 4. Highest Educational Level

01. Primary  02. Secondary  03. Tertiary

### 5. Marital Status

01. Married  02. Single  03. Divorced  04. Widowed  05. Engaged

6. How many years have you been qualified? \_\_\_\_\_ (*please specify*)

### 7. Do you have a certificate of neonatology?

01. Yes  02. No

8. How many years you are working in NICU ? \_\_\_\_\_ (*please specify*)

Before you completing the survey, please answer the following question, then go on to the Section B. Do you practice KC in NICU in any way? (Circle your response)

1. NO

2. YES

## SECTION B : Kangaroo Care (KC) Survey

**Instruction:** Please answer the following questions. Use the following scale for your responses:

5 = Strongly Agree

4 = Agree

3 = Neither Agree Nor Disagree

2 = Disagree

1 = Strongly disagree

### Part I : Perception on KC

No	Statement	5	4	3	2	1
1	All preterm babies should be allowed to participate in KC regardless of age.					
2	All preterm babies should be allowed to participate in KC regardless of weight.					
3	Babies receiving IV fluids should NOT be allowed to participate in KC.					
4	Babies who are intubated should NOT be allowed to participate in KC.					
5	Babies with umbilical catheters should NOT be allowed to participate in KC.					
6	Babies on ventilators should NOT be allowed to get KC.					
7	Babies with chest tubes should NOT be allowed to get KC.					
8	KC encourages the parenting role.					
9	KC enhances the attachment process between mother and baby.					
10	KC increases the quality of care on your unit.					
11	KC interrupts baby care\ giving.					
12	KC should be available only to breastfeeding mothers.					
13	KC is NOT feasible with some babies.					
14	KC keeps nurses too tied to the bedside.					
15	KC should be offered to all mothers in the NICU.					
16	KC will benefit preterm babies.					
17	KC will help mothers feel more confident in caring for their preterm baby.					
18	KC will improve the baby's outcome.					
19	KC will interfere with the completion of my tasks.					
20	Learning about KC will help me be a better nurse.					
21	Nurses look forward to introducing KC to a new mother.					
22	Our babies have adequate time for mother-baby contact without the use of KC.					
23	The increased amount of time required to prepare a baby for a KC session is out of proportion to the benefits.					
24	The teamwork required between nurses and mothers when doing KC is worth the effort.					
25	There is NOT enough flexibility in the NICU to allow parents extended visits (more than 1 hours) for KC.					

## Part II : Knowledge on KC

**Instruction:** Please answer the following questions to the best of your ability based on your own **personal knowledge** of KC, **NOT** on its practice. Circle your response that best represent to knowledge of KC. Use the following scale for your responses:

3 = True

2 = False

1 = Not sure

No	Statement	True	False	Not sure
1	Babies appear to be satisfied in KC.	3	2	1
2	Babies on oxygen therapy experience a decrease in oxygen saturation.	3	2	1
3	Babies on phototherapy can participate in KC.	3	2	1
4	Babies on anotrope/vasopressor should NOT participate in KC.	3	2	1
5	Babies typically experience more bradycardia episodes during KC.	3	2	1
6	Babies with peripheral IVs can participate in KC.	3	2	1
7	KC has been shown to improve breathing patterns in preterm babies by reducing apnea.	3	2	1
8	KC is contraindicated in babies less than 28 weeks gestation.	3	2	1
9	KC is contraindicated in babies weighing less than 1000 grams.	3	2	1
10	KC is now considered safe as an alternative approach to care for medically stable, continuing care preterm babies.	3	2	1
11	Most babies experience a decrease in temperature during KC.	3	2	1
12	Published reports of clinical observations indicate that the rate of accidental extubation is higher with KC than with traditional methods of holding.	3	2	1
13	Research has indicated that babies who receive KC increase their mother's milk supply.	3	2	1
14	Research indicates that KC promotes quiet sleep.	3	2	1
15	Research shows that babies with arterial lines should NOT participate in KC.	3	2	1
16	The most physiologically stressful part of KC for the baby is the transfer to the mother's chest.	3	2	1
17	There is an increased risk of infection in the baby with KC.	3	2	1
18	Research shows that babies with Drug Withdrawal have less agitation during KMC than when NOT in KC.	3	2	1
19	Babies with some congenital heart defects have physiologic stability in KC.	3	2	1
20	Babies on ventilators mode do well during KC.	3	2	1

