## **1.6 Hypothesis**

The following hypotheses guided the study:

- $H_1$ : A KC-EP can improve perception, knowledge, and perceived barriers in relation to KC, and levels of stress among mothers.
- $H_2$ : KC is effective in improving weight gain patterns, LOS, and breastfeeding rates among premature infants.
- $H_3$ : A KC-EP can improve nurses' perception, knowledge, and practice in relation to KC implementation.

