***b) Part II: Mother's Knowledge on Kangaroo Care***

Part II of the mother's knowledge questionnaire was adapted from the original KCQs tool developed by Arthur J. Angler, & Eileen Brumbaugh, Ludington-Hoe, et al. (2013) with slight modifications so as to be relevant and meet the objectives of the mothers' outcomes. There were similar knowledge questionnaires for the mothers and nurses regarding their ability to implement KC. Mothers were requested to circle a number and indicate their opinion on their knowledge of KC. The scoring was from not sure (1) to false (2) and true (3). The items were worded in both positive and negative terms (Table 3.3). Positive items answered with 'true' were considered correct and incorrect if they were answered 'false' or 'not sure'. Out of 11 items, there were six positive statements, which were (1,2,4,6,7,8), and five negative statements, which were (1,2,3,5,11). A higher score indicated a higher level of knowledge with reference to the descriptors. Higher mean scores of  $M=2.03$  and above-indicated mothers had a good level of knowledge regarding KC, while lower mean scores below  $M=2.03$  indicated a poor level of knowledge on KC.

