***b) Part II: Nurses' Knowledge of Kangaroo care***

The Part II questionnaire was on nurses' knowledge, determined by 20 true-false items to assess nurses' knowledge pertaining to initiation of KC with preterm infants in the NICU setting. The items were adopted from the KCQ tool developed by Arthur J. Angler & Eileen Brumbaugh, Ludington-Hoe et al. (2013). Nurses had to grade their level of knowledge according to 'not sure' (1), 'false' (2) and 'true' (3). These items were selected because they contained sufficient information to evaluate or report on the KC-related knowledge of mothers and infants. The items were worded in a positive and negative way. Positive items answered as 'true' were considered correct and if answered 'false' or 'don't know' were considered incorrect. The negative items were reversely rated. Out of 20 items there were 11 positive statements, which were (4,6,7,8,9,10,13,14,15,18,19), and nine negative statements, which were (1,2,3,5,11,12,16,17,20). The scores for knowledge were converted into mean scores, and then classified into two parts. Higher mean scores of  $M=2.34$  and above indicated good knowledge, while mean scores below  $M=2.34$  indicated poor knowledge and experiences in relation to KC in the NICU.

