## Indication infants for Kangaroo Care(Cont.)

- Incubator / open air crib - can maintain (36.8 – 37.4 °C)
- Stable in low rate ventilator
- Dosages of medications have stabilized
- No O2 supplement or with low O2
- Consistently taking milk well.
- Gain weight (15 – 20 grams/day for 3 - 5 days/ 10 – 15 gram/day)
- Infant with phototherapy – Mother presses the fiber - optic blankets against the infant's back while doing KC.

22

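### The nurses' knowledge key reverse-rates two statements that the course teaches as true, so the H3 knowledge gain can be biased downward

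*Combined protocol and SAP*

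**What the plan says.** H3 (section 1.6) reads "A KC-EP can improve nurses' perception, knowledge, and practice in relation to KC implementation". Knowledge is thus one of three nurse outcomes. It is measured before and about a week after the course in a single group of 47 nurses, with no control nurses.

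Section 3.10.1, Part II (Nurses' Knowledge) gives the response code: "Nurses had to grade their level of knowledge according to 'not sure' (1), 'false' (2) and 'true' (3"). *True* is correct on positive items, while *false* or *don't know* is incorrect. Negative items are reverse-rated, but the mapping is not printed. Eleven items are listed as positive (4, 6, 7, 8, 9, 10, 13, 14, 15, 18, 19), and there are "nine negative statements, which were (1,2,3,5,11,12,16,17,20"). A mean of 2.34 or more counts as good knowledge.

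In Appendix H, Part II, item 1 is "Babies appear to be satisfied in KC" and item 3 is "Babies on phototherapy can participate in KC".

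The theory slides in Appendix P list, under indications, "Infant with phototherapy – Mother presses the fiber - optic blankets against the infant's back while doing KC". Phototherapy does not appear on the contraindications slide. The slide on the position of the baby says that infants cry less and are more at ease, and the oxytocin and amygdala slide links kangaroo care to calm and contentedness.

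**The concern.** Items 1 and 3 favour kangaroo care, and the course supports them, but the printed key treats them as statements to be rejected. A nurse who takes in the teaching then gets less than full credit on these items. A nurse who gives up a *false* answer because of the teaching scores as if she had got worse.

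The error lies in which answer is credited, so it would survive a switch from 1/2/3 coding to right/wrong marking. It works against H3: the before-after gain would be understated, and the good/poor split at 2.34 would rest on scores that partly penalise the taught answers.

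**Working it through.** **1. The plan's own count.** The 11 positive and 9 negative items do not overlap and together cover items 1 to 20, so 11 + 9 = 20 is reproduced. The key is complete; the question is where items 1 and 3 sit.

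**2. Is *negative* only a label for wording?** No. Items 4 and 15 contain NOT and are keyed positive; items 1, 3 and 20 are affirmative and keyed negative. The list works as an answer key, and elsewhere it follows the slides: items 8 and 9 (contraindications), 7 and 14 (infant benefits) and 13 (milk supply) are positive, while 11 (hypothermia rare) and 17 (fewer infections) are negative. Items 1 and 3 depart from that pattern.

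**3. Scores.** Assume the other 18 items are answered as keyed. Because the reversal is undefined, three readings are shown: (a) right/wrong; (b) 4 − x on negative items; (c) *true* and *false* codes swapped on negative items, *not sure* = 1.

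| Answer to items 1 and 3 | (a) | (b) mean | (c) mean |
|---|---|---|---|
| *false* (as keyed) | 20/20 | (11×3 + 9×2)/20 = 51/20 = 2.55 | 60/20 = 3.00 |
| *true* (as taught) | 18/20 | (11×3 + 7×2 + 2×1)/20 = 49/20 = 2.45 | 58/20 = 2.90 |
| *not sure* | 18/20 | (11×3 + 7×2 + 2×3)/20 = 53/20 = 2.65 | 56/20 = 2.80 |

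If both items were re-keyed as positive (13 positive, 7 negative), *true* on both would give 20/20, (13×3 + 7×2)/20 = 2.65, and 3.00.

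**4. Before-after change under the printed key.**

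- *False* to *true* on both: −2 marks (10 percentage points) under (a); −0.10 under (b) and (c).
- *Not sure* to *true* on both: 0 under (a); 2.65 to 2.45 = −0.20 under (b); 2.80 to 2.90 = +0.10 under (c).
- *True* at both tests: no change under any reading.

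Under (a), with both items re-keyed, the first nurse would gain 2 marks and the second would also gain 2. The error in measured gain is therefore 4 marks, 2 marks and 0 for the three patterns. The documents give no pretest answers, so the group average cannot be fixed within that range.

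**5. The cut-off.** Under (b) the nurse who answers as taught scores 2.45, which is 0.11 above 2.34; under (c) she is far above it.

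**6. Item 20.** It says that ventilated babies do well and is also keyed negative. The slide offers only "Stable in low rate ventilator", which is conditional. Including it would give 17/20 and, under (b), 48/20 = 2.40, a *false*-to-*true* fall of 0.15. It is not counted in the result.

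**7. The mothers' key.** The same two statements are the mothers' items 1 and 2. Section 3.8.1, Part II says "there were six positive statements, which were (1,2,4,6,7,8"), but the same sentence then gives the negatives as 1, 2, 3, 5 and 11. Items 1 and 2 are in both lists; items 9 and 10 are in neither.

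**The case against.** Several points on the other side stand.

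- A reader might infer that the 2.34 split misclassifies trained nurses. The documents do not show this: the worked nurse is still rated good under both mean-score readings.
- A reader might put the loss at 0.20 to 0.30 on the mean. That compares the score under the printed key with the score under a corrected key, and the upper end needs item 20. The before-after fall from *false* to *true* is 0.10.
- It is not generally true that learning is scored as decline. That depends on the pretest answer and on the undefined reversal. The mean figures under 4 − x also rest on a reading that gives *not sure* the top mark on negative items.
- The mothers' list might seem to confirm that the items are positive. It lists them both ways and supports neither key. It also raises the possibility that the nurses' list is a misprint of the key actually used; the source tool's key is not in the documents.
- The documents are not uniform on phototherapy. Section 3.7.1 excludes infants on prolonged phototherapy, section 3.16.4 a) removes experimental-group infants who need it, and section 3.10.1, Part III lists the phototherapy practice item (item 8) as negative. Appendix H does ask for knowledge rather than practice, and study eligibility is not course content, but these passages rule out simply declaring item 3 positive.
- For item 1, the slides support the statement by close paraphrase, not in the same words.

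None of this explains why the printed key withholds full credit for what the course teaches.

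**Conclusion.** The concern holds in a limited form. As printed, the key denies full credit for the taught answer on items 1 and 3 under every reading of the reversal tried here: 18/20 against 20/20, or 0.10 below the as-keyed mean. The H3 knowledge gain can be biased downward, by nothing for nurses who already answered *true* and by a 2-mark fall for those who move from *false* to *true* on both. The size for the group depends on pretest answers and on the scoring rule, neither of which is given. The 0.10 assumes that the other 18 items are answered as keyed.

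Severity is moderate: two firm items of 20, in one of three nurse outcomes. For nurses moving to the taught answer, the bias under right/wrong scoring runs against the hypothesis. No view is taken on which infants should receive kangaroo care.

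**What to change.** Before scoring:

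1. Move item 1 to the positive list in section 3.10.1, Part II.
2. Reconcile item 3 across that section, Appendix H, the indications slide in Appendix P, sections 3.7.1 and 3.16.4 a), and the practice list in section 3.10.1, Part III. Reconcile item 20 with the ventilator line on the indications slide. The final key should agree with what the course teaches.
3. Score every item correct or incorrect against that key, with *not sure* incorrect; this also removes the undefined reversal.
4. Recompute the totals and the 2.34 cut-off, and state how the cut-off is derived.
5. Correct the mothers' key in section 3.8.1, Part II, so that each of the 11 items appears in exactly one list.

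If the key actually applied differs from the printed one, print the applied key and confirm it against the slides. The cost is an edited answer key and a re-score of existing answers; no new data are needed.

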### Part III : Practice on KC

**Instruction:** Please describe how comfortable are you to initiate KC on baby with the following items? Use the following scale:

5 = Very Comfortable

4 = Somewhat Comfortable

3 = Neither Comfortable Nor Uncomfortable

2 = Somewhat Uncomfortable

1 = Very Uncomfortable

No.	Statement	5	4	3	2	1
1	Baby with intravenous catheters.					
2	Baby during the perioperative period.					
3	Baby with endotracheal intubation.					
4	Baby with high-frequency rate or ventilator mode.					
5	Baby with nasal cannula oxygen (nasal prong).					
6	Baby with Nasal Continuous Positive Airway Pressure (NCPAP).					
7	Baby with percutaneous central lines.					
8	Baby with phototherapy treatment.					
9	Baby with Umbilical Arterial Catheters (UAC).					
10	Baby with Umbilical Venous Catheters (UVC).					
11	Baby with anotrope/vasopressors.					

**Appendix I: Structured kangaroo care educational program (KC-EP) for nurses.**

 UNIVERSITY OF MALAYA	Course contents of kangaroo care education programme (KC-EP) for Nurses
Educational Program Session:	All nurses in neonatal intensive care unit (NICU), University Malaya Medical Centre (UMMC).
Course: Course Title:	Neonatal Health Nursing Physiology of kangaroo care (KC) and benefits for infant – mother dyads.
Medium of Instruction:	English and Bahasa Malaysia
Teaching materials/ Equipment	Laptop, LCD, white board, marker pen, lecture notes, showing video, pamphlets, booklet, incubator, thermometer, dummy, baby sling/tube, diapers, infant cap, mother's outfit (open in front), all related forms/diary applicable to the topic presentation and red & blue ball point.
Learning	Lecture (show and tell), Practical (skill) & Discussion
Student Learning Time	Face to face (interpersonal communication): 8 hours Guide learning(theory): 4 hours Assessment(practical) : 4 hours
Soft Skills	Communication skills Problem solving skills Teamwork skills Information Management Professional Ethic and Moral
Presenter e-mail address	[name] [contact] @ [contact]
Theory Session: Day : Time :	Friday & Sunday 2.00pm – 6.00pm
Practical session: Day : Time : Venue :	Monday, Tuesday, Wednesday, Thursday and Saturday and including public holiday 08.00am – 5.00pm Conference Room, Neonatal Intensive Care Unit, University Malaya Medical Centre, Klang Valley

## Appendix J : Contents of structured kangaroo care educational program (KC-EP) for nurses.

 UNIVERSITY OF MALAYA	Course contents of kangaroo care education programme (KC-EP) for nurses.
Educational Program Session (Participant)	All nurses in neonatal intensive care unit (NICU), University Malaya Medical Centre.(UMMC)
Course: Course Title:	Kangaroo care education programme (KC-EP) for nurses Physiology of kangaroo Care and benefits for infant – mother dyads.
Medium of instruction	English and Bahasa Malaysia
Teaching materials/aids Equipment	Laptop, LCD, hand out, white board, marker pen, lecture notes, showing video, pamphlets, booklet, incubator, thermometer, infant dummy, baby sling/tube, diapers, infant cap, mother's outfit (open infront), all related forms/diary applicable to the topic presentation and red & blue ball point.
Mode of teaching Learning strateexperimental groupies	Lecture-demonstration Lecture (show and tell), Practical (skill) & Question and Answer
Student Learning Time	Face to face (interpersonal communication): 8 hours Guide learning(theory): 4 hours Assessment(practical) : 4 hours
Presenter e-mail address	[name] [contact] @ [contact]
Theory Session: Day/Time: Venue:	Every Friday and Sunday (August –September 2018) 2.00 pm – 6.00pm Conference Room, Neonatal Intensive Care Unit, University Malaya Medical Centre, Klang Valley
Practical session: Day/Time:	Every Monday, Tuesday, Wednesday, Thursday, Saturday and including public holiday (August – September 2018) 08.00am – 5.00pm
Pre-requite knowledge	Anatomy and Fundamental of Nursing - Integumentary system - Reproductive system - Digestive system - Cardiovascular system - Cardiopulmonary system - Central nervous system - Neonatal and pediatric nursing - Nurses have knowledge on giving care and treatment to the preterm babies (feeding)
General objective :	At the end of the program the nurse will be able to have in depth understanding of physiology and benefits of Kangaroo Care in detail and demonstrate the technique as well.
Specific objectives :	At the end of the program the nurses will be able to : 1) define the term and dose of kangaroo care (KC). 2) explain the physiology and method of KC. 3) state the benefits of KC to infant-mother dyads. 4) state the indication and contraindication for KC (eligibility criteria). 5) state the guidelines and protocols before, during and after the KC method. 6) recognize sign and symptoms of deterioration among premature infant before, during and after the method. 7) state the preparation before, during and after the KC method. 8) list the equipment for KC method ; 8.1 for infant 8.2 for mother 9) educate and guided on chart/record the infant progress record /diary 10) demonstrate and return-demonstrate the kangaro care method.
Important Date	Pre-test & Post-test (7 th day after pretest and KC-EP for nurses)

